- bb. Adverse events are collected following signing of the informed consent form at Screening through the last study visit (FU)

CONFIDENTIAL Page 17 of 56

- cc. Perform identification and susceptibility testing at local laboratory for *Candida* for any positive blood culture or positive culture from a specimen obtained from a normally sterile site at Screening and for any positive culture requiring a change of antifungal therapy (ie, identification and susceptibility testing not required for *Candida* isolates cultured from specimens obtained on other study days without a required change in antifungal therapy).
- dd. Blood for culture must be obtained as part of the standard of care for inclusion in the study. Established mycological diagnosis of candidemia and/or IC sufficient for inclusion in the study is defined as ≥1 blood culture positive for yeast or *Candida*, a Sponsor-approved rapid IVD test positive for *Candida* spp, or a positive Gram stain for yeast or positive culture for *Candida* spp. from a specimen obtained from a normally sterile site ≤96 hours before randomization. Record species and susceptibilities for all bacteria isolated within 1 week prior to randomization from blood or any other normally sterile site. If the positive blood culture used to qualify the subject for the study is drawn >12 hours from randomization, then an additional set of blood cultures must be obtained ≤12 hours before randomization.
- ee. Obtain blood and/or normally sterile tissue/fluid for culture if demonstrating mycological eradication or if clinically indicated. Blood cultures should be repeated daily (preferred) or every other day until 2 negative blood cultures are obtained ≥12 hours apart, without an intervening positive culture. All fungal isolates cultured from blood and normally sterile tissue/fluid from Screening through the last study visit must be sent to the Central Laboratory. Record the species and susceptibilities for any new bacteria isolated from blood or any other normally sterile site.

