The overall success rate is the proportion of subjects with success out of the total number of subjects evaluated.

CONFIDENTIAL Page 19 of 56

Mycological Response

Mycological response will be programmatically determined from the electronic case report form (eCRF) and central mycology data at Day 5, Day 14 (± 1 day), Day 28 (± 2 days; only for subjects with IC) and FU (Days 45-52 or Days 52-59 for subjects with IC), according to the definitions in Table 1-3. Determination of the identification of fungal pathogens will follow the process defined in SAP Section 4.

Table 1-3: Mycological Response Definitions

Mycological Response	Definition	
Success (eradication/presumed eradication) *	 If positive blood culture at baseline: The last blood culture drawn on or prior to the day of assessment and another blood culture drawn at least 12 hours prior are both negative for Candida spp and both blood cultures were drawn after initiation of study drug, AND 	
	 Any intervening blood cultures drawn between the 2 qualifying negative blood cultures are also negative for Candida spp. 	
	 If positive culture from a normally sterile site at baseline: Documented mycological eradication: culture on day of assessment from all normally sterile sites of baseline Candida infection (if accessible) is negative OR if no culture on the day of assessment, the most recent culture obtained after the initiation of study drug is negative, OR 	
	o Presumed mycological eradication: follow-up culture is not available (eg, normally sterile baseline site of Candida infection not accessible) or the most recent culture obtained after the initiation of study drug is positive in a subject with a successful clinical outcome (ie, did not receive rescue antifungal treatment and has resolution of systemic signs of invasive candidiasis that were present at baseline) and resolution or improvement of any baseline radiographic abnormalities due to invasive candidiasis,	
	 AND There was no change of antifungal therapy for the treatment of candidemia and/or invasive candidiasis, AND 	
	The subject is not lost to follow up on the day of assessment.	
	Note : Subjects with positive cultures from both blood and a normally sterile site will need to meet success criteria for both blood and normally sterile site to be considered success.	

CONFIDENTIAL Page 20 of 56

Mycological Response	Definition		

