- All-cause mortality (ACM) through the FU Visit: defined as death due to any cause from the date and time of randomization through the FU Visit. Subjects who did not die or are lost to follow-up will be censored in the analysis at the last date known to be alive.
- Time to negative blood culture: defined as the time, in hours from the first dose of study drug to the first of 2 negative blood cultures drawn ≥12 hours apart following the first pre-treatment blood culture confirmed positive for any *Candida* species. Determination of the identification of fungal pathogens will follow the process defined in SAP Section 4. Subjects will be censored at the earliest start date and time of receipt of an alternative antifungal (ie, other than study drug) for the treatment of candidemia received any time on/after the date and time of the first dose of study drug. If a subject is lost to follow-up prior to having 2 negative blood cultures, the subject will be censored at the date of the last blood culture.

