2. SUBJECT POPULATION

2.1. Population Definitions

The following analysis populations will be evaluated and used for presentation and analysis of the data:

- Intent-to-Treat (ITT) Population: All subjects randomized to treatment. A subject is considered randomized when a randomization transaction has been recorded in the IWRS, regardless of whether the subject actually receives study drug.
- Safety Population: All subjects randomized to treatment and who received any amount of study drug.
- Microbiological Intent-to-treat Population (mITT): A subset of subjects in the Safety population with documented *Candida* infection based on a Central Laboratory evaluation of an isolate from a blood culture obtained within 96 hours of randomization or from a specimen obtained from a normally sterile site. Determination of the identification of fungal pathogens will follow the process defined in SAP Section 4.
- Microbiological Intent-to-treat 2 Population (mITT2): A subset of subjects in the mITT population had documented *Candida* infection based on Central Laboratory evaluation of:
 - o a culture from blood drawn within 12 hours prior to randomization or within 72 hours after randomization; OR
 - o a culture from another normally sterile site obtained within 48 hours prior to randomization or within 72 hours after randomization.
- Microbiological Intent-to-treat 3 Population (mITT3): A subset of subjects in the mITT population who had documented *Candida* infection based on Central Laboratory evaluation of:
 - o a culture from blood drawn within 12 hours prior to randomization or within 72 hours after randomization; OR
 - o a culture from another normally sterile site obtained within 96 hours prior to randomization or within 72 hours after randomization.
- Pharmacokinetics (PK) Population: All CD101 treated subjects with at least 1 plasma sample obtained for PK analysis.

Demographics (including age, race, and gender), diagnosis (candidemia and/or IC), medical history, baseline assessments, mycological data, systemic signs and symptoms, and administration of study drug will be summarized for the ITT population, unless otherwise specified. The Safety population is the primary population for the analysis of safety endpoints. All efficacy analyses will be conducted in the mITT population, unless otherwise specified. A select set of efficacy analysis will also be perfomed in the mITT2 and mITT3 populations.

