3.4. Baseline Definitions

For all analyses with exception of the analysis involving attributable systemic signs, baseline will be defined as the most recent measurement prior to the first administration of study drug. In the event the screening visit and treatment administration occur on the same date, baseline will be defined as measurements obtained at the screening visit.

All blood and normally sterile site samples taken 96 hours before randomization will be used to determine the presence of *Candida* at baseline. In instances where multiple samples of the same type occur with the same pathogen within 96 hours before randomization, the sample with highest MIC to study drug will be used as baseline pathogen.

For attributable systemic signs, all assessments of signs taken in the period 4 hours prior to the draw of the qualifying blood culture (when systemic signs of infection resulted in obtaining blood cultures), qualifying positive culture from a sterile site, or qualifying rapid IVD, through the first dose of study drug will be used to determine the presence of attributable systemic signs at baseline.

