5.3.3.2. Time to Negative Blood Culture

The time to negative blood culture (hours) will be analyzed using Kaplan-Meier methodology by treatment group, and for the CD101 treatment groups combined, in the mITT population. Summaries will include the 25th, 50th (median), and 75th percentiles. The number and percentage of subjects censored and the reason for censoring (receipt of more than 1 dose of non-study antifungal for the treatment of candidemia and/or IC [with the exception of a rescue antifungal],

CONFIDENTIAL Page 41 of 56

lost to follow up prior to having 2 negative blood cultures) will also be provided. A graph of the Kaplan-Meier curves will be provided.

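### Time to negative blood culture is counted from first dose but does not require post-dose negatives, so an event can fall before time zero; its risk set is also not limited to blood-positive subjects

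*SAP*

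**What the plan says.** - **Definition (SAP 1.2.6.1).** The outcome is "defined as the time, in hours from the first dose of study drug", so time zero is the start of study treatment. The event that stops the clock is "the first of 2 negative blood cultures drawn ≥12 hours apart following the first pre-treatment blood culture confirmed positive for any" *Candida* species. Two censoring rules follow: start of an alternative antifungal for candidemia, and loss to follow-up before two negatives. Nothing is said about negatives drawn before the first dose, or about a positive culture between the two negatives.
- **Culture timing (SAP 1.2.5; Table 1-1 footnote dd; 3.4).** The qualifying sample may date from up to 96 hours before randomization. If the qualifying blood culture is more than 12 hours old, "then an additional set of blood cultures must be obtained ≤12 hours before randomization". For baseline status, "All blood and normally sterile site samples taken 96 hours before randomization will be used to determine the presence of" *Candida*. Section 1.2.2 places randomization on Day 1 just ahead of dosing, so the repeat set is drawn before treatment.
- **Mycological response (SAP Table 1-3).** For success in blood, the plan requires that "both blood cultures were drawn after initiation of study drug", and that any culture between the two is also negative. Table 1-6 puts the same post-initiation condition on its single culture.
- **Analysis (SAP 5.3.3.2).** Kaplan-Meier percentiles and curves are produced "by treatment group, and for the CD101 treatment groups combined, in the mITT population". Under Section 2.1, a subject enters mITT on an isolate from a "blood culture obtained within 96 hours of randomization or from a specimen obtained from a normally sterile site".

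**The concern.** The clock and the event have different starting points. Time zero is the first dose, but the only lower bound on the qualifying negatives is the first pre-treatment positive, which may be days earlier. The plan itself requires a culture in that gap for many subjects, and Table 3-1 foresees prior antifungal therapy of 24 hours or more. A pre-dose negative is therefore a foreseeable result.

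The plan does not say whether the resulting negative time is dropped, set to zero, or replaced by the first post-dose negative. Two programmers could report different medians from the same data.

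The second limb concerns who is at risk. A subject with only a sterile-site isolate has no pre-treatment positive blood culture, so the event has no anchor. Neither censoring rule covers that subject.

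**Working it through.** The SAP gives no event count, expected clearance time or precision for this outcome, so there is no figure to reproduce. The check applies the definition literally and then illustrates how far handling could matter.

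**1. A subject already negative before dosing.** First dose is T = 0. Blood cultures: positive at −72 h, negative at −10 h (the required repeat set), negative at +14 h and +38 h.
- Literal definition: the first two negatives after the pre-treatment positive are −10 h and +14 h, which are 24 h apart (≥12 h). Time = **−10 h**.
- Both negatives post-dose, as in Table 1-3: the pair is +14 h and +38 h, again 24 h apart. Time = **+14 h**.

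Only the first of the two negatives has to be pre-dose for the problem to arise.

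**2. A positive in between.** Cultures: positive at −72 h, negative at −10 h, positive at +14 h, negative at +38 h and +62 h. Section 1.2.6.1 omits the no-intervening-positive condition, so its wording does not exclude pairing −10 h with +38 h, giving −10 h for a subject still culture-positive on drug. The Table 1-3 conditions give +38 h.

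**3. Sterile-site isolate only.** No pre-treatment positive blood culture exists, so the time is undefined. The subject has neither an alternative antifungal start nor loss to follow-up, so neither censoring rule applies.

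**4. Illustration; all frequencies are assumed.** Arms of 30 (the Part A planning figure in Section 3.1); exponential clearance with median 36 h; a share *f* whose first negative falls 0–12 h before dosing. Under the post-dose rule, these subjects' first post-dose negative falls 6–30 h after dosing. Mean Kaplan-Meier median over 2,000 simulated arms (35.2 h at *f* = 0):

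| *f* | negative times kept | negative times dropped | both negatives post-dose |
|---|---|---|---|
| 10% | 29.5 h | 36.7 h | 30.2 h |
| 20% | 23.6 h | 35.1 h | 26.7 h |
| 30% | 16.9 h | 37.0 h | 24.0 h |

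Check on the second column: solving (1 − *f*)·2^(−t/36) = 0.5 gives t = 36·log2(2(1 − *f*)) = 30.5, 24.4 and 17.5 h. This agrees apart from small-sample error.

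For sterile-site-only subjects, with no pre-dose negatives: if they make up 10% or 20% of the arm, leaving them out gives medians of 36.9 and 34.8 h. Keeping them as censored at 1,200 h gives 40.9 and 49.1 h.

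**The case against.** **A time from first dose is naturally read forward.** On this view the reference to a pre-treatment positive only identifies who has the endpoint, and the text is silent on pre-dose negatives. That is a fair reading, and it defeats the inference that the plan deliberately counts pre-treatment clearance as drug effect. It does not remove the gap. The SAP states the post-dose condition where it wants it (Tables 1-3 and 1-6), omits it here, and gives no rule for a negative time.

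**Sterile-site-only subjects may simply drop out.** Section 3.2 bases displayed sample sizes on non-missing values, and the mITT label repeats the efficacy default. This stands to the extent that a reader should not infer that the plan counts these subjects as never clearing. The limb is a missing restriction, and weaker than the first.

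**The harm depends on one handling.** A reader might infer a spurious arm difference. With *f* at 25% and 35% and negative times set to zero, the same model gives 36·log2(1.5) = 21.1 h against 36·log2(1.3) = 13.6 h. That 10-point gap is within one standard error at 30 per arm: √(2·0.3·0.7/30) = 0.118. But if negative times are dropped, both arms stay at 36 h. The 7.4 h gap (21.06 − 13.63) is also shorter than one daily culture interval, and randomization balances *f* in expectation. The documents do not support a claim of actual bias.

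**mITT2 or mITT3 might look like the remedy.** They are not. Both admit sterile-site positives and blood positives up to 72 hours after randomization, so neither guarantees a positive blood culture at first dose.

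**Conclusion.** The point holds as a defect of definition. Read literally, Section 1.2.6.1 can date the event before time zero, and the plan's own repeat-culture requirement makes this foreseeable. Section 5.3.3.2 does not limit the risk set to subjects who can have the event.

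The size cannot be derived from the SAP, because neither the frequency of pre-dose negatives nor the number of sterile-site-only subjects is given. In the illustration the median moves by a few hours to about 20 h according to handling (16.9 h kept against 37.0 h dropped at *f* = 30%), but every input except the arm size is assumed.

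The outcome is additional and descriptive, with no between-arm test planned, and no alpha or sample size depends on it. Severity is minor.

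A reader might go further and conclude that only subjects positive at their last pre-dose culture belong in the analysis. The documents do not compel that. The plan's standard for clearance in blood is two negatives, and the second worked subject, still positive at +14 h, would be wrongly removed after a single negative.

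**What to change.** 1. In Section 1.2.6.1, define the event as the first of two *Candida*-negative blood cultures at least 12 hours apart, both drawn after the first dose of study drug and with no positive between them, consistent with Table 1-3.
2. In Section 5.3.3.2, restrict the analysis to mITT subjects with at least one *Candida*-positive pre-treatment blood culture.
3. Report by arm the number excluded for having no positive blood culture and the number whose last pre-dose culture was already negative. The second count is needed because the post-dose rule makes the time usable but still records such subjects as clearing early (24.0 h at *f* = 30% in the illustration, against 35.2 h at *f* = 0).
4. Optionally, add a sensitivity analysis in subjects positive at the last pre-dose culture, noting that it drops some who are still candidemic after one negative.

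The cost is a few lines of SAP text, a little programming on culture times already used for mycological response, and slightly fewer subjects in this outcome.

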1.2.5. Study Procedures

After informed consent is obtained, all potential study participants undergo screening evaluations, which include a medical history, clinical assessments, and laboratory assessments. Mycological diagnosis of candidemia at Screening will be established by ≥1 blood culture positive for yeast or *Candida* spp., a Sponsor-approved rapid IVD test positive for *Candida* spp., or a positive Gram stain for yeast or a positive culture for *Candida* spp. from a specimen obtained from a normally sterile site from a sample taken within 96 hours before randomization. If the positive blood culture used to qualify the subject for the study is drawn >12 hours from randomization, then an additional set of blood cultures must be obtained ≤12 hours before randomization. Assessments of mycological eradication and clinical response will be performed at Day 5, Day 14 (±1 day), Day 28 (±2 days) for subjects with IC and the FU visit (Days 45-52 or Days 52-59 for IC subjects). Blood cultures should be performed daily or every other day until 2 blood cultures drawn ≥12 hours are negative without an intervening positive culture. The schedule of assessments and procedures, as outlined in the study protocol, is presented in Table 1-1.

Study participation will require from 45 to 52 days (or 52-59 days for subjects with IC) after the first administration of study drug; study drug administration from Day 1 up to Day 21 (for subjects with candidemia) or up to Day 28 (±2 days; only for subjects with IC); PK assessments on Days 1, 2, 4, 8, and 15; safety, tolerability, and efficacy assessments up to Day 21 (for subjects with candidemia only) or up to Day 28 (±2 days; only for subjects with IC); and a FU visit at Days 45 to 52 (or 52-59 days for subjects with IC).

CONFIDENTIAL Page 13 of 56

Table 1-1: Schedule of Assessments and Procedures

							Study 1	Drug A	dminis	tration,	Days						FU Visit
Study Day (window)	Screen	1 ^a	2	3	4	5	6, 7	8 ^b (±1)	9-13	14 ^b (±1)	15 ^b (±1)	16-21	22 ^{b,c} (±1)	23- 27°	28 ^{b,d} (±2)	EOT +2 days after last dose of study drug (IV and oral)	only (or Day 52-
Informed consent e	X							,		,	,		,		,	,	,
Medical history ^f	X																
Physical examination including height and weight ^g	X									X					X		X
Calculate Child-Pugh score h	X																
Modified APACHE II score with Glasgow coma score ⁱ	X																
Vital signs ^j	X	X	X	X	X	X	X ^k	X	X ^k	X	X ^k	X ^k	X	X^k	X	X	X
12-lead ECG ¹	X															X	

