Failure	 If positive blood culture at baseline: The last blood culture drawn on or prior to the day of assessment or any blood culture drawn prior to and within 12 hours of the last blood culture is positive for Candida spp and both blood cultures were drawn after the initiation of study drug OR The most recent blood culture drawn at least 12 hours prior to the last blood culture is positive for Candida spp. and culture was obtained after the initiation of 		
	study drug. OR If positive culture from a normally sterile site at baseline: Documented mycological persistence: culture on day of assessment from all		
	normally sterile sites of baseline Candida infection (if accessible) is positive, OR		
	o Presumed mycological persistence: follow-up culture is not available (eg, normally sterile baseline site of Candida infection not accessible) or the most recent culture obtained after the intiation of study drug is positive in a subject without a successful clinical outcome or with continued (from baseline) radiographic abnormalities due to invasive candidiasis,		
	OR • The subject requires a change of antifungal therapy to treat candidemia, OR		
	The subject dies of any cause prior to or on the day of assessment.		
Indeterminate	• If positive blood culture at baseline: A blood specimen was not available to culture or the result was not available.		
	• If positive culture from a normally sterile site at baseline: A sterile site/fluid post-baseline specimen was not available to culture or the result was not available AND an assessment of signs of invasive candiasis was not available.		
* D 1 1' .'	Subject is lost to follow-up on the day of assessment.		

^{*} Presumed eradication is defined only for a culture from a normally sterile site and is not defined for a blood culture.

Table 1-4 provides examples of timing of the blood cultures and how these are used for determination of the mycological response.

CONFIDENTIAL Page 21 of 56

Table 1-4: Examples of Timing of Blood Cultures

	Blood Cultures	Mycological Response [1]
Example 1	Day of Assessment: Day 14 (T=0 hours) Blood cultures: T=0 (N), T= -18 (N)	Success (eradication)
Example 2	Day of Assessment: Day 14 (T=0 hours) Blood cultures: T=0 (N), T=-10 (P) T=-18 (N)	Failure
Example 3	Day of Assessment: Day 14 (T=0 hours) Blood cultures: T= -20 (N), T= -28 (N) T= -34 (P)	Failure

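### Time to negative blood culture: the censoring rule and the tabulated censoring reasons disagree, death before clearance is not covered, and the event does not exclude an intervening positive culture

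*SAP*

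**What the plan says.** **Event.** Section 1.2.6.1 starts the clock at the first dose of study drug. The event is "the first of 2 negative blood cultures drawn ≥12 hours apart following the first pre-treatment blood culture confirmed positive" (meaning positive for *Candida*). It sets no condition on cultures taken between the two negatives.

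**Censoring rule.** The same section states: "Subjects will be censored at the earliest start date and time of receipt of an alternative antifungal (ie, other than study drug) for the treatment" (candidemia only), at any time from the first dose. Its only other rule begins "If a subject is lost to follow-up prior to having 2 negative blood cultures" and censors such a subject at the last blood culture.

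**Analysis and reporting.** Section 5.3.3.2 specifies Kaplan-Meier analysis in the mITT population by treatment group and for the CD101 groups combined. "Summaries will include the 25th, 50th (median), and 75th percentiles", and the number censored is reported by reason. Two reasons are listed. One is loss to follow-up before two negatives. The other is "receipt of more than 1 dose of non-study antifungal for the treatment of candidemia and/or IC [with the exception of a rescue antifungal".

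**Related definitions.** Section 1.2.5 has blood cultures continue "until 2 blood cultures drawn ≥12 hours are negative without an intervening positive culture". Table 1-3 requires for mycological success: "Any intervening blood cultures drawn between the 2 qualifying negative blood cultures are also negative for" *Candida*. Footnotes ee and gg of Table 1-1 carry the same condition. Table 1-3 classes a change of antifungal therapy to treat candidemia, and death from any cause, as failure; loss to follow-up is indeterminate. The Clinical Response text of Section 1.2.6.1 counts rescue for candidemia before Day 14 as clinical failure.

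**The concern.** There are three separate problems.

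1. The rule that censors subjects and the list that reports why they were censored describe different sets of subjects, and the SAP does not say which governs. Two programmers could produce different curves and different censoring counts.
2. Death before clearance has no rule, nor does completing follow-up without two qualifying negatives. Censoring at rescue is stated, and is likely to be informative: Kaplan-Meier assumes that a censored subject would have gone on to clear like those still at risk, whereas a subject rescued for candidemia has left because study drug did not suffice. Censoring deaths would do the same. The curve could then show higher clearance than was achieved on study drug.
3. Read literally, the event lets a subject whose culture turned positive again count as cleared from the first negative.

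**Working it through.** The SAP gives no event count, rescue rate, death rate or clearance time for this outcome, so there is no stated figure to reproduce. The text comes first, then an illustration on assumed data.

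**Step 1. The two censoring statements side by side**

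| Subject, before clearance | Section 1.2.6.1 | Section 5.3.3.2 reason list |
|---|---|---|
| One non-study dose for candidemia | Censored at its start | No category (needs more than 1 dose) |
| Rescue antifungal for candidemia | Censored at its start | Excepted, so no category |
| More than 1 non-study dose for IC only, not rescue | Not censored | Listed as a reason |
| Lost to follow-up | Censored at last blood culture | Listed |
| Death | No rule | Not listed |
| Completes without two negatives | No rule | Not listed |

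Death cannot be read as loss to follow-up, because Table 1-3 puts the two in different categories.

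**Step 2. Effect of censoring at rescue or death (assumed data)**

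Assume n = 30 blood-culture-positive subjects, of whom k are rescued, or die and are censored, while still positive. The others clear at 24/48/72/96/120/144/168 h in these numbers:

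- k=1: 10, 7, 5, 3, 2, 1, 1
- k=3: 9, 7, 4, 3, 2, 1, 1
- k=6: 8, 6, 4, 2, 2, 1, 1

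Let m be the number uncleared just before the rescue or death time, and x the number of the others who clear from then to 120 h. Censoring overstates clearance by 120 h by (x/n) × k/(m−k), compared with counting the k subjects as not cleared.

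At 84 h:

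- k=1: (5/30)(1/7) = 2.4 points; 92.4% against 27/30 = 90.0%
- k=3: (5/30)(3/7) = 7.1 points; 90.5% against 25/30 = 83.3%
- k=6: (4/30)(6/6) = 13.3 points; 86.7% against 22/30 = 73.3%

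| Time of rescue or death | k=1 | k=3 | k=6 |
|---|---|---|---|
| 84 h | 2.4 | 7.1 | 13.3 |
| 60 h | (10/30)(1/12) = 2.8 | (9/30)(3/11) = 8.2 | (8/30)(6/10) = 16.0 |
| 36 h | (17/30)(1/19) = 3.0 | (16/30)(3/18) = 8.9 | (14/30)(6/16) = 17.5 |

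At 168 h censoring gives 100% for every k. Counting as not cleared gives 29/30 = 96.7%, 27/30 = 90.0% and 24/30 = 80.0%.

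**Step 3. The planned percentiles (25th/50th/75th, h), censored against not cleared**

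| Time | k=1 | k=3 | k=6 |
|---|---|---|---|
| 84 h | 24/48/96, same | 24/48/96, same | 24/72/120 vs 24/72/144 |
| 60 h | 24/48/96, same | 24/48/96, same | 24/72/96 vs 24/72/144 |
| 36 h | 24/48/72 vs 24/48/96 | 24/48/96, same | 24/48/96 vs 24/72/144 |

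Nothing moves in five of the nine scenarios, and the median moves in one.

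A second assumed data set points the same way. Of 30 subjects, 8, 6, 4 and 3 clear at 24, 48, 72 and 120 h, and the other 9 never clear. If k of those 9 are censored at 36 h, estimated clearance by 120 h is 0.77 (k=3) or 0.86 (k=6), against 21/30 = 0.70 when they are kept as not cleared. For k=6 the median is 48 h instead of 72 h.

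**Step 4. The event rule**

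Table 1-4 Example 2 has a negative at −18 h, a positive at −10 h and a negative at 0 h, and labels it Failure. Place T=0 at 48 h after the first dose (an assumption; the SAP's example is a Day 14 assessment). The cultures are then N at 30 h, P at 38 h and N at 48 h. The outer negatives are 48 − 30 = 18 h apart, so the event as written occurs at 30 h. With the no-intervening-positive condition there is no event by 48 h. If a further culture at 72 h (also assumed) is negative, the event time is 48 h.

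**The case against.** The strongest reply is that Section 1.2.6.1 is the definition and Section 5.3.3.2 only a parenthetical list for a table, so the definition governs and the list needs tidying. Similar wording about more than one dose, with rescue excepted, defines excluded subsets in Sections 3.8, 5.3.1 and 5.3.2, so it may have been carried over. That is plausible but nowhere stated. Even on that reading, rescued and single-dose subjects are censored without a category to report them in.

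Clearance on study drug, censored at other therapy, can also be defended as a deliberate choice, and the failure rules cited belong to visit-based responses, where rescue and death are already counted. It is true that those rules do not formally bind this outcome. But the choice does not make the censoring non-informative, and death has no rule under any reading.

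Two further points are fair. Right-censoring at the end of observation is the usual default for subjects who never clear, so on its own that gap is only a missing date. And a reader who knows the sampling rule would probably take the two negatives as uninterrupted; still, the SAP states that condition in its other definitions and not in this one.

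The sizes are wholly assumed. Clearance by 120 h is not a planned summary, and the k=1 shift at 36 h reflects the 24-hour grid (75.4% against 73.3% cleared at 72 h). These points limit the practical weight and leave the textual defects standing.

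**Conclusion.** The concern holds. The two sections cannot both be followed for rescued, single-dose or IC-only subjects; death before clearance has no rule; and the event as written accepts a culture pattern that the SAP elsewhere labels Failure. On the assumed data, censoring overstates clearance by about 2 to 3 points with one affected subject in 30 and by 13 to 18 points with six. The 25th percentile never moves, and the median and 75th move only in some scenarios. For rescue, these figures follow from the stated censoring rule; for death, they apply only if deaths are censored. The actual size depends on rescue and death rates that the SAP does not give. Because the outcome is additional and descriptive, no power, alpha or primary result is affected. It should be corrected before unblinding, so that the rule is not chosen after the curves are seen.

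A wording point only: unlike Table 1-3, the definition does not state that both negatives are drawn after the first dose, although measuring time from that dose suggests it.

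**What to change.** - Reconcile Sections 1.2.6.1 and 5.3.3.2 into one analysis rule that states dose count, indication and the handling of rescue, and use the same reasons in the censoring table.
- If clearance on study drug is meant, treat rescue or alternative antifungal therapy for candidemia or IC, and death, before clearance as not cleared. Either keep these subjects at risk without an event to the end of the time scale, or treat them as competing events and report cumulative incidence. If clearance regardless of rescue is meant, say so and do not censor at rescue.
- Censor for loss to follow-up. For subjects who complete without two qualifying negatives, censor at the last blood culture or at the end of follow-up, and state which.
- Define the event as the first of two negative blood cultures, both drawn after the first dose and at least 12 hours apart, with no positive culture between them.

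This concerns the analysis only; which antifungal use is clinically appropriate is not at issue. The cost is minor SAP wording and programming, with no new data. Reported clearance may be lower than under the present censoring rule.
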